9.1.3. Unscheduled Visits

All attempts should be made to keep patients on the study schedule. Unscheduled visits may be necessary to repeat testing following abnormal laboratory results, for follow-up of AEs, or for any other reason, as warranted.

9.2. Study Procedures

9.2.1. Procedures Performed Only at the Screening/Baseline Visit

The following procedures will be performed for the sole purpose of determining study eligibility or characterizing the baseline population:

- Obtain informed consent (including optional sub-studies)
- Review inclusion/exclusion criteria
- Record demographics
- Record medical history. Medical history should include detailed cardiovascular and pancreatitis history.
- Record prior medications (within 12 weeks prior to screening)

- Perform physical examination
- Measure height and weight for BMI calculation
- Blood sample for serum amylase and lipase
- Blood sample to assess FSH to verify postmenopausal status, if applicable
- Blood sample to assess free thyroxine (FT4) and TSH to evaluate thyroid function and diagnose thyroid diseases
- Mandatory DNA sample for FCS genotyping for patients who have no documentation of prior genotype testing that confirms the absence of FCS due to LoF mutations in *LPL*

9.2.2. Efficacy Procedures

9.2.2.1. Acute Pancreatitis Episodes

The primary efficacy measurement in this study is the occurrence of AP in any study patient at any time during the DBTP as reported by the investigator and adjudicated by the APAC (see diagnostic criteria in Section 5.2.1).

Patients will receive an emergency card to take with them to the hospital in the event of AP. The card will inform the hospital staff that the patient is a participant in a clinical trial and include contact information for the investigator.

9.2.2.2. Fasting Blood Samples for Assessment of Lipid Profile (For Efficacy and PD Variables)

All laboratory samples will be collected before the dose of study drug is administered.

Blood samples for lipid panels should be collected in the morning, in fasting condition (ie, overnight, at least an 8-hours fast, only water) for all clinic visits. Medications are permitted to be taken with water as medically indicated. Alcohol consumption within 48 hours, and smoking or intense physical exercise within 24 hours, preceding blood sampling are discouraged.

Note: If the patient is not in the fasting condition, the blood sample should not be collected, and a new appointment can be scheduled the day after (or as close as possible to this date) with a reminder to be fasted. Patients who are not fasted should 1) be reminded that they should fast, and 2) should be seen by study staff the next day or as close as possible in a fasted state.

Fasting blood samples will be collected at specified time points listed in [Table 1](#) for assessment of the standard lipid profile, including plasma TG, LDL-C by direct measurement, HDL-C, non-HDL-C, and TC. As TG values may exceed 400 mg/dL (4.52 mmol/L), LDL-C will be measured via the beta quantification method (rather than via the Friedewald formula).

The specialty lipid panel (ApoC3, ApoB48, ApoB100, ApoB Total) will be assessed with a separate sample that is collected at applicable visits. The standard lipid panel and specialty lipid panel will be directly measured by the central laboratory.

Detailed procedures of sample preparation, storage, and shipment are provided in the laboratory manual.

9.2.2.3. NMR Lipid Profile

Lipoprotein particle concentrations will be measured by NMR.

9.2.2.4. Clinical Outcome Assessments

9.2.2.4.1. Presence of Abdominal Pain

The Presence of Abdominal Pain questionnaire is a single-item, dichotomous questionnaire which will be used to determine if abdominal pain was present in the 7 days before the visit. The item asks the following question: “Did you have abdominal pain related to your disease during the past week?” If the patient answers ‘yes’ to this question, they will be asked to complete the HAP-Pain questionnaire.

9.2.2.4.2. HAP-Pain

The abdominal pain patient-reported outcome to be used in this study is the HAP-Pain questionnaire, which contains 4 items that measure aspects of pain due to AP. The HAP-Pain has a 7-day recall period. Each question is rated on an 11-point scale with 0 indicating ‘no pain’ and 10 indicating ‘worst possible pain.’ Patients will complete the HAP-Pain questionnaire at each visit if they answer ‘yes’ on the Presence of Abdominal Pain questionnaire.

9.2.3. Safety Procedures

9.2.3.1. Vital Signs and Body Weight

Vital signs, including temperature, sitting blood pressure, pulse, and respiration, will be measured pre-dose and at other time points at visits according to [Table 1](#) and [Table 2](#). Body weight (kg) and height will be measured at screening for BMI determination. Weight (to be recorded to the nearest 0.1 kg) will also be measured during the DBTP ([Table 1](#)) and off-drug follow-up period ([Table 2](#)).

Patients will be closely monitored for a minimum of 60 minutes after IV administration of study drug.

9.2.3.2. Physical Examination

A thorough and complete physical examination will be performed at time points according to [Table 1](#). Care should be taken to examine and assess any abnormalities that may be present, as indicated by the patient’s medical history.

9.2.3.3. Electrocardiogram

Electrocardiograms should be performed before blood is drawn during visits requiring blood draws. A standard 12-lead ECG will be performed at time points according to [Table 1](#) and [Table 2](#). A 12-lead ECG should be performed in the supine position after resting for at least 10 minutes. For each ECG recording throughout the study, the electrodes should be positioned in the same place as much as possible. The ECG will be interpreted locally by the investigator. Heart rate will be recorded from the ventricular rate, and the PR, QRS, RR, QTcB, and QTcF intervals will be recorded. Any clinically significant abnormality should be documented as an AE/SAE as applicable. Each ECG tracing will be analyzed in comparison with the screening record trace. The ECG strips or reports will be retained with the source.

9.2.3.4. Laboratory Testing

Hematology, chemistry, and serum pregnancy testing samples will be analyzed by a central laboratory. Urine pregnancy testing samples will be analyzed locally (patients will use a pregnancy test provided by the site for phone visits in the follow-up). Detailed instructions for blood sample collection are in the laboratory manual provided to study sites.

Samples for laboratory testing will be collected at visits according to [Table 1](#) and [Table 2](#). Tests will include:

Blood Chemistry

Sodium	Total protein, serum	Total bilirubin
Potassium	Creatinine	Uric acid
Chloride	Blood urea nitrogen (BUN)	Creatine phosphokinase (CPK)
Carbon dioxide	Aspartate aminotransferase (AST)	Phosphorus
Calcium	Alanine aminotransferase (ALT)	Magnesium
Glucose	Alkaline phosphatase	
Albumin	Lactate dehydrogenase (LDH)	

Note: Blood chemistry should be performed after the patients have fasted for at least approximately 8 hours at the visits defined in the Schedule of Events.

Hematology

Hemoglobin	Differential:
Hematocrit	Neutrophils
Red blood cells (RBCs)	Lymphocytes
White blood cells (WBCs)	Monocytes
Red cell indices	Basophils
Platelet count	Eosinophils

Other Laboratory Tests

- Pregnancy testing (WOCBP only): serum human chorionic gonadotrophin (β -HCG) pregnancy testing at screening, and urine pregnancy testing at all subsequent scheduled visits
- Pregnancy testing and contraception are not required for women with documented hysterectomy or tubal ligation.
- Postmenopausal women must be amenorrheic for at least 12 months in order not to be considered of childbearing potential. Follicle-stimulating hormone will be measured for verifying postmenopausal status, as applicable.
- Blood sample for FT4 and TSH

Abnormal Laboratory Values and Laboratory Adverse Events

All laboratory values must be reviewed by the investigator or authorized designee.

Significantly abnormal test results that occur after start of treatment must be repeated to confirm the nature and degree of the abnormality. When necessary, appropriate ancillary investigations should be initiated. If the abnormality fails to resolve or cannot be explained by events or conditions unrelated to the study medication or its administration, the medical/study director must be consulted.

The clinical significance of an abnormal test value, within the context of the disease under study, must be determined by the investigator.

Criteria for reporting laboratory values as an AE are provided in Section 10.1.1.

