Study Procedure														
Electrocardiogram ⁸	X	X												
Adverse Events	X	X	X	X	X	X	X	X	X	X	X	X	X	X
Laboratory: ⁵														
Hematology	X	X												
Blood Chemistry	X	X	X	X		X		X		X		X		X
Pregnancy Test ^{9,10}	X	X	X	X	X	X	X	X	X	X	X	X	X	X
Pharmacokinetics and Immunogenicity Sampling:														
Drug Conc. Sample ¹¹		X	X	X	X	X	X	X	X	X	X	X	X	X
ADA and NAb sample ¹²		X				X				X				
Biomarkers:														
Biomarker		X							X					
Serum/Plasma ¹³														
Lipoprotein Analysis by NMR		X												
Optional Pharmacogenomics:														
DNA Sample (Optional) ¹⁴		X												
Other:														
Mandatory DNA Sample for FCS	X													
Genotyping for Subset of Patients ¹⁵														
Dietary Review	X	X	X	X	X	X	X	X	X	X	X	X	X	X
Alcohol Intake Review	X	X	X	X	X	X	X	X	X	X	X	X	X	X

Table 2: Schedule of Events for the Off-Drug Follow-up Period

	End of DBTP	Off Drug Follow-Up		
		V15	V16	End of Study V17
Visit # (V)	V15	V16		End of Study V17
Week	52	62		72
Day	365	435		505
Window (day)	±4	±7		±7
Efficacy:				
Lipid Profile ¹	X	X	X	
Special Lipids ¹	X		X	
Presence of Abdominal Pain (1-Item Question)	X	X	X	
HAP-Pain Questionnaire	X	X	X	
Safety:				
Concomitant Meds and Treatment	X	X	X	
Weight	X	X	X	
Vital Signs	X	X	X	
Physical Examination			X	
Electrocardiogram ²			X	
Adverse Events	X	X	X	
Laboratory : ³				
Hematology	X		X	
Blood Chemistry	X	X	X	
Pregnancy Test ^{4,5}	X		X	
Pharmacokinetics and Immunogenicity Sampling: ⁶				
Drug Conc. Sample	X		X	
ADA and NAb Sample	X		X	
Biomarkers:				
Biomarker Serum/Plasma	X		X	
Lipoprotein Analysis by NMR	X			
Other:				
Dietary Review	X	X	X	
Alcohol Intake Review	X	X	X	

9.1.1. Footnotes for the Schedule of Events Tables**9.1.1.1. Footnotes for Table 1 Schedule of Events (DBTP)**

1. Medical history should include detailed cardiovascular and pancreatitis history.
2. Height will be measured in meters (m). Body weight will be assessed using calibrated scales. Patients should void (empty bladder) prior to weight assessment. Patients should be wearing undergarments only and no shoes during weight assessments. Body weight will be recorded to the nearest 0.1 kg. Body mass index (BMI) is calculated as weight (kg)/height(m)².
3. Postmenopausal status will be confirmed by measurement of FSH.
4. At dosing visits, all assessments (including urine or serum pregnancy tests for WOCBP) should be performed before the dose of study drug is administered.

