9.1.1.2. Footnotes for Table 2 Schedule of Events (Off Drug Follow-up Period)

1. Lipids and lipoproteins (Lipid Profile): TC, TG, HDL-C, LDL-C will be measured. Special lipids: ApoC3, ApoB48, ApoB100, ApoB Total.
2. Electrocardiograms should be performed before blood is drawn.
3. All samples should be collected following at least an 8-hour fast. Medications are permitted to be taken with water as medically indicated.
4. Pregnancy test for WOCBP: A urine test will be done at all other visits indicated. Any positive urine test should be confirmed with a serum pregnancy test.
5. All patients will be reminded of protocol-specified contraception use and pregnancy reporting.
6. Drug concentration should occur prior to and at the end of infusion of study drug, if applicable. Immunogenicity collection should occur prior to infusion of study drug, if applicable.

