11.4.5.1. Adverse Events

All AEs reported in this study will be coded using the currently available version of the Medical Dictionary for Regulatory Activities (MedDRA®). The verbatim text, the preferred term (PT), and the system organ class (SOC) will be provided in patient listings.

Definitions

For safety variables, the following observation periods are defined:

- The pre-treatment period is defined from the day the ICF is signed to the day before the first dose of double-blind study treatment.
- The TEAE observation period is defined from the day of the first dose of double-blind study treatment to the day of the last dose of double-blind study treatment + 168 days (24 weeks) (residual effect of treatment for IV dose regimen is expected until 24 weeks after the last dose of study drug).

The post-treatment observation period is defined as the time from the day after the end of the TEAE period to the last study visit.

Treatment-emergent adverse events are defined as those adverse events that developed, worsened, or became serious during the TEAE period.

Analysis

Adverse event incidence tables will present data by SOC sorted alphabetically and PT sorted by decreasing frequency, and summarize the number (n) and percentage (%) of patients experiencing an AE. Multiple occurrences of the same event in the same patient will be counted only once in the tables. Data conventions for missing or partial AE dates will be addressed in the SAP. The denominator for computation of percentages is the SAF population within each treatment group.

Summaries of TEAE incidences will include:

- All TEAEs
- All treatment-emergent SAEs, including patient deaths
- All treatment-emergent AESIs
- TEAEs by severity (according to the grading scale outlined in Section 10.2.5), depicting the worse TEAE severity for those patients with multiple occurrences of the same event
- All TEAEs leading to permanent treatment discontinuation

An AE patient listing will be provided for all patient deaths occurring during the TEAE period and the post-treatment period.

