**Table 3: Schedule of Events for the Off-Drug Follow-up Period**

Visit # (V)	End of DBTP	Off Drug Follow-Up		
		V15	V16	End of Study V17
Week	52	62		72
Day	365	435		505
Window (day)	±4	±7		±7
Efficacy:				
Lipid Profile 	X	X	X	
Special Lipids 	X		X	
Presence of Abdominal Pain (1-Item Question)	X	X	X	
HAP-Pain Questionnaire	X	X	X	
Safety:				
Concomitant Meds and Treatment	X	X	X	
Weight	X	X	X	
Vital Signs	X	X	X	
Physical Examination			X	
Electrocardiogram 			X	
Adverse Events	X	X	X	
Laboratory : 				
Hematology	X		X	
Blood Chemistry	X	X	X	
Pregnancy Test 	X		X	
Pharmacokinetics and Immunogenicity Sampling: 				
Drug Conc. Sample	X		X	
ADA and NAb Sample	X		X	
Biomarkers:				
Biomarker Serum/Plasma	X		X	
Lipoprotein Analysis by NMR	X			
Other:				
Dietary Review	X	X	X	
Alcohol Intake Review	X	X	X	

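### Protocol Table 2 leaves the week-62 clinic visit (V16) without a urine pregnancy test that Section 9.2.3.4 calls for, so a site following the table schedules none for 20 weeks

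*Protocol*

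**What the plan says.** Protocol Section 9.2.3.4 (Laboratory Testing) contains three statements that bear on this:

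- In the bullet on women of childbearing potential, a serum test at screening is followed by "urine pregnancy testing at all subsequent scheduled visits".
- More generally, "Samples for laboratory testing will be collected at visits according to" Tables 1 and 2.
- On local urine testing, "patients will use a pregnancy test provided by the site for phone visits in the follow-up".

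Table 1 marks the test at screening and at every dosing visit, weeks 0 to 48. Table 2 marks it at V15 (week 52) and V17 (week 72) and leaves V16 (week 62) empty. Footnote 4 to Table 2 reads "A urine test will be done at all other visits indicated". SAP Table 3 copies the same pattern.

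Sections 6.1 and 8.3.2 describe two in-clinic visits in the off-drug period, and Section 8.3.2 identifies them as V16 and V17. Section 6.1 also commits to monitoring pregnancy status throughout the study and for 20 weeks after the last dose.

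**The concern.** The bullet in Section 9.2.3.4 and the row in Table 2 give different instructions for V16. A site could follow either in good faith.

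The blank falls in a period the protocol treats as one of continuing exposure. Section 3.3.1 names embryofetal toxicity as a potential risk, based on animal studies. Section 11.4.5.1 sets the treatment-emergent period on the ground that "residual effect of treatment for IV dose regimen is expected until 24 weeks after the last dose of study drug". Exclusion criterion 19 (contraception) and Section 10.1.3 (pregnancy reporting) use the same 24 weeks. Under Table 2, scheduled testing changes from every 4 weeks to a single 20-week interval inside that window. A pregnancy the patient has not recognised could go without a scheduled test until the last study visit.

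Patients who stop drug and withdraw early are sent to the V16 and V17 columns by Section 8.3.2, so the blank reaches them too.

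**Working it through.** **Reading the table.** The text form of Table 2 has a stray empty column in its header, so the position of the blank was checked against other rows. Blood chemistry, weight and lipid profile each carry three marks (V15, V16, V17). The pregnancy row carries two with an empty cell between them, which places the blank at V16. Section 9.1.2 calls the week-52 visit visit 16, but Table 2 and Section 8.3.2 both make V16 the first off-drug visit. That numbering is used here.

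**Inputs**

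| Item | Day | Window | Source |
|---|---|---|---|
| Last scheduled dose (week 48) | 337 | ±4 | Table 1 |
| V15 (week 52) | 365 | ±4 (361 to 369) | Table 2 |
| V16 (week 62) | 435 | ±7 (428 to 442) | Table 2 |
| V17 (week 72) | 505 | ±7 (498 to 512) | Table 2 |

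**The plan's own figure.** Off-drug period = (505 − 365)/7 = 20.0 weeks, as Section 6.1 states.

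**Position relative to the last dose.** V15: (365 − 337)/7 = 4 weeks. V16: (435 − 337)/7 = 14 weeks. V17: (505 − 337)/7 = 24 weeks. The 24-week window ends on Day 337 + 168 = 505.

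**Interval without a scheduled test under Table 2**

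- Nominal: 505 − 365 = 140 days (20.0 weeks).
- Shortest with windows: 498 − 369 = 129 days (18.4 weeks).
- Longest with windows: 512 − 361 = 151 days (21.6 weeks).
- Against the Table 1 interval: 140/28 = 5 times.
- Share of the 24-week window: 140/168 = 83%.

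**The 20-week commitment in Section 6.1.** Twenty weeks after the last dose is Day 337 + 140 = 477. The earliest in-window V17 is Day 498. The week-52 test is therefore the only one Table 2 schedules within those 20 weeks.

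**With a test at V16**

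- V15 to V16: 435 − 365 = 70 days nominal; 428 − 369 = 59 to 442 − 361 = 81 days with windows.
- V16 to V17: 505 − 435 = 70 days nominal; 498 − 442 = 56 to 512 − 428 = 84 days with windows.
- Scheduled tests fall 4, 14 and 24 weeks after the last dose.

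**Gain in scheduled detection.** A pregnancy already detectable at V16 is picked up 505 − 435 = 70 days sooner; one that becomes detectable later gains 0 days. The documents do not say how onset is distributed, so the possible average is anywhere from 0 to 70 days. If detectability is assumed to begin evenly over Days 365 to 505, then 70/140 = 50% gain 70 days, and the average is 0.5 × 70 = 35 days (5 weeks).

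The interval for early withdrawals depends on the date of the early termination visit and is not computed.

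**The case against.** The documents allow a reading under which nothing conflicts. Section 9.2.3.4 defers to the tables and footnote 4 limits urine tests to marked visits, so the bullet may only be contrasting serum at screening with urine afterwards. V16 also omits hematology, special lipids, drug concentration and anti-drug antibodies, so the blank may be intended. If so, rewording the bullet would be enough. This reading is reasonable, and the blank cannot be called a proven error. But rewording would leave the 20-week interval in place, with only the week-52 test inside the 20 weeks of monitoring promised in Section 6.1.

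The comparison with 4-weekly testing also needs its context. During dosing, the test precedes each infusion and a positive result stops the drug (Section 8.3.2.1). After week 48 there is no dose to withhold, so a week-62 test can only bring forward reporting and counselling. That stands, and it lowers the stakes.

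Other safeguards remain: required contraception, reminders at visits and calls, adverse event questioning at V16, unscheduled visits and 24-hour pregnancy reporting. The 35-day average ignores all of these and should not be read as actual delay in detection. The documents give neither the number of women of childbearing potential nor a pregnancy rate, so the number affected is unknown. SAP Section 1 records the August 2022 decision to discontinue the study for poor recruitment, which further limits it.

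**Conclusion.** The concern holds as a minor safety-monitoring correction. Text and table differ on V16, and a site following the table leaves a nominal 140 days (129 to 151) without a scheduled pregnancy test after a week-48 last dose. Almost all of that falls within the 24-week window the protocol sets for residual effect, contraception and reporting. The interval rests only on the visit days and windows in Tables 1 and 2. The 35-day average gain rests on an assumption of even onset that is not in the documents. Dosing, endpoints and efficacy inference are unaffected. Confidence is medium, because the blank may be deliberate.

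**What to change.** Mark the urine pregnancy test at V16 (week 62) in Protocol Table 2. Carry the mark to SAP Table 3 for consistency only, since the SAP copy does not govern site testing. Keep the home-test wording in Section 9.2.3.4: no phone visit is scheduled in follow-up, but Sections 6.1 and 9.1 allow phone contact under the COVID-19 contingency.

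The cost is one mark in each table and one extra locally read urine test per woman of childbearing potential. It needs no new visit, blood draw or change to the analysis. The longest interval between scheduled tests falls to 70 days nominal, and at most 84 days with windows.

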9.2.4. Drug Concentration and Measurements

Samples for concentrations of total evinacumab and total ANGPTL3 in serum will be collected at visits listed in [Table 1](#) and [Table 2](#).

Any unused samples may be used for exploratory biomarker research.

9.2.5. Immunogenicity Measurements and Samples

Samples for ADA and NAb assessments will be collected at visits listed in [Table 1](#) and [Table 2](#). They will be collected pre-dose on days when study drug is administered. Any unused samples may be used for exploratory biomarker research.

9.2.6. Pharmacodynamic and Exploratory Biomarker Procedures

In this study, research assessments will be performed to explore how evinacumab may modify TG-rich lipoprotein metabolism underlying the risk of recurrent AP in patients with HTG and a recent history of HTG-associated AP. In particular, the role of inhibition of ANGPTL3 and the effect of evinacumab on PD markers or biomarkers will be explored.

Biomarker samples will be collected at time points according to [Table 1](#) and [Table 2](#). Pharmacodynamic marker/biomarker measurements will be performed to determine effects on biomarkers of HTG or relevant physiological and pathogenic processes. The biomarkers studied are believed to be relevant to the pathophysiology of indication, target engagement, mechanism of action of evinacumab, and possible toxicities.

9.2.7. DNA Sample for FCS Genotyping

For patients without documentation of prior genetic testing that confirms the absence of FCS due to LoF mutations in LPL, a required blood sample for DNA isolation will be collected to identify or confirm known mutations in LPL, APOC2, APOA5, LMF1, and GPIHBP1, the genes implicated in FCS, and results will be reported back to the investigator.

Patients who have FCS due to LoF mutations in LPL as determined by the screening genotyping will be considered screen failures. The presence of mutations in other genes implicated in FCS (APOC2, APOA5, LMF1, GPIHBP1) will be determined for informational purposes and will not exclude patients from participating. This includes double heterozygote patients, with an LoF mutation in *LPL* and an LoF mutation in another FCS-related gene.

